Trial Protocol

Title: "Longitudinal trial assessing cellulite in women wearing a new compression garment - one side with ink printed micro-pads ("Vari-pads") and one side without."

Principal Investigator: [name] MS FRCS(Gen) FCPhleb

Protocol Identifying Number: TWC-SM-2023-01

Protocol version number & date: v 1.1 28 June 2023

Ethics: Not required according to HRA Decision Tools (see Result - England Ethics 21-May-

2023) – and confirmed by e-mail from MHRA.

NCT: To be registered on ClinicalTrials.gov on confirmation of Ethics position

Background:

Cellulite is a very common condition that affects up to 90% of women.¹ It is much less commonly found in men. It presents as a dimpling principally of the skin of the buttocks and thighs, with the appearance having been described as resembling "orange peel", "cottage cheese" or a "quilt". In women who are affected, it usually appears after puberty. It occurs in all races, but is thought to occur more commonly in Caucasians.¹

The product being tested:

The product being tested is to be a retail (non-medical) product presented as standard compression shorts with a pattern of small, raised pads ("Vari-pads") of different heights printed on the inner aspect. A previous trial that we have performed has suggested that wearing these for eight hours a day can reduce the appearance of cellulite.² In addition, subjects found these compression pants to be very comfortable.²

In this trial, we want to see whether the subjective and objective improvement is due to the compression alone, or whether the Vari-pads on the inside of the product enhance the subjective or objective impression of cellulite. As such, we have asked the manufacturer to produce pairs of pants where the Vari-pads are printed onto the inner aspects as per usual on one side only, but not on the other side.

Subjects will then be asked to wear the apparel for at least eight hours a day, at times most suitable for themselves.

If and when they notice a difference between the appearance of cellulite between the two sides, they will notify us and we will then swap them into the 'normal' garments with Vari-pads on both sides, which they are then welcome to continue to wear.

Subjects:

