We will be asking for volunteers of who are adult women (over the age of 18 years old), who are able to walk normally and have cellulite of their buttocks and/or upper thighs. We will ask them to check the inclusion and exclusion criteria and, if they believe that they are able to be part of the trial, they will be given an appointment to see the trial coordinator.

Inclusion Criteria:

- Women, over the age of 18 years old, who are able to walk normally and who have cellulite on their buttocks and/or upper thighs.

Due to having to produce special garments for this trial where only half of the garment has the Vari-pads, there will be for following restrictions:

Total number = 60

Volunteers will be asked their sizes (Small, Medium, Large and Extra-large) and will only be invited to attend if there are available places in that size category.

Sizes:

- Small = 15
- Medium = 15
- Large = 15
- Extra-large = 15

Exclusion Criteria:

- Women under 18 years of age.
- Women who are pregnant or who intend to get pregnant in the next 6 months.
- Women with no discernible cellulite on initial examination.
- Women undergoing any other treatment which aims to reduce the appearance of cellulite.
- Women who are unable to complete at least 3 months of this trial.

The Trial:

Volunteers will be asked to email their interest in the trial and will be asked to check that they fit the inclusion and exclusion criteria. If they do, they will be given a free of charge appointment.

Potential volunteers will then be sent the subject information sheet by email so they have ample opportunity to both read about the trials but in addition, to ask any questions before their first appointment. These can be answered by email. In this way, we hope that most volunteers will be suitable to proceed with the trial. We will stop recruitment when a maximum 60 subjects have been enrolled.

The garments will be worn for at least 8 hours per 24 hours. For hygiene reasons, we suggest that briefs/pants are worn under the garment. However, to increase the area of contact between garment and cellulite, we suggest wearing a thong, "high thigh", or similar panties.

There will be 4 visits required:

- 1] First Visit Start of trial
- 2] 3 Months Visit
- 3] 6 Months Visit End of trial

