- 4] Variable end-point visit whenever the subject can tell that there is a difference between the left and right sides if the subject does not reach this end point, they will only have 3 visits and will not need the garment with Vari-pads on both sides.

First Visit (day zero):

Subjects will be asked to sign a consent form if they have asked sufficient questions and have decided to go ahead with the trial.

- Their cellulite will be graded as per the Nürnberger F, Müller grading system³

Grading	Description
Scale	
0	No alteration to the skin surface - NO CELLULITE SO THESE
	SUBJECTS will be EXCLUDED
1	Skin is smooth whilst subject is standing/lying, but alterations can be seen
	by pinching the skin, or by muscle contraction
2	'Orange-peel' or mattress appearance is evident upon standing without the
	use of any manipulation (pinching or muscle contraction)
3	Alterations seen in grade two presented together with raised areas and
	nodules

- Standard high-resolution photographs will be taken of their buttocks from behind, side and obliquely in the standing position with the muscles relaxed. The same will then be performed for the thighs. [Subjects will not be photographed in any way so as to be able to identify them.]
 - Subjects will have height and weight measured and noted.
- Localised transcutaneous water content measurement using LymphScanner (Delfin Technologies, Finland) this is a non-invasive device passed over the skin to determine the electrical conductance of the skin and sub-cutaneous tissues.
- They will be given a Celluqol[®] Quality of life questionnaire (long version see appendix)⁴ to complete.
- They will then be given the garment (x2) with one side covered with the Vari-pads, with the other side without any raised pads.

Variable End-point Visit:

When subjects can see or feel a significant difference in the cellulite of their buttocks and/or thighs between the sides, they will contact us and return for assessment.

At this visit, the following will be performed:

- Weight
- Photographs
- Questions as to the routine of garment wearing how many hours per 24 and when
- Transcutaneous water content buttocks and thighs
- Celluqol® QOL Questionnaire
- They will be given 2 new garments with Vari-pads on BOTH sides.

3 Months Visit.

At this visit, the following will be performed:

- Weight
- Photographs
- Questions as to the routine of garment wearing how many hours per 24 and when
- Transcutaneous water content buttocks and thighs

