- Cellugol® QOL Questionnaire

6 Months Visit - end of trial and £100 paid if all visits completed. The subject can keep the x2 bilaterally padded garments.

At this visit, the following will be performed:

- Weight
- Photographs
- Questions as to the routine of garment wearing how many hours per 24 and when
- Transcutaneous water content buttocks and thighs
- Celluqol® QOL Questionnaire

Primary endpoint:

- The time taken for patients to notice a self-determined significant difference between their right and left side and request the full garment.

Secondary endpoints:

- Quality of life changes by Celluqol® questionnaire 0, 3 and 6 months.
- Changes in photographs 0, 3, 6 months as assessed by 2 'blinded' observers
- Changes in transcutaneous water measurements

Interim Analysis:

We will perform an initial analysis when all of the results are in from the 1 month and 3 months visit.

Consent form: Please see attached.

Subject information sheet: Please see attached.

Insurance: The Whiteley Clinic has full insurance cover for clinical trials.

Payment: Subjects who complete the trial to 6 months will be allowed to keep the compression garments (worth £90.00 each) and will be given £100 in compensation for their time and travel.

References:

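### Follow-up photographs and water readings have no fixed time since garment removal, although baseline is unworn, so transient wear effects could enter the only blinded or instrument-based endpoints (minor)

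*Protocol*

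**What the plan says.** The garment is a pair of compression shorts carrying "a pattern of small, raised pads" on the inside, in this trial on one side only (The product being tested). Duration of wear is fixed but timing is not: "Subjects will then be asked to wear the apparel for at least eight hours a day, at times most suitable for themselves". The Trial section suggests brief underwear "to increase the area of contact between garment and cellulite", so the pads bear on the area that is later photographed.

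At the First Visit, photographs and transcutaneous water content are listed first. The garment comes last: "They will then be given the garment (x2) with one side covered with the Vari-pads". Photographs are standardised for view and posture, "in the standing position with the muscles relaxed". The Variable End-point, 3 Months and 6 Months visits repeat photographs and water content, and their only item on wear is "Questions as to the routine of garment wearing how many hours per 24 and when".

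The Secondary endpoints include "Changes in photographs 0, 3, 6 months as assessed by 2 'blinded' observers" and "Changes in transcutaneous water measurements".

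**The concern.** The primary endpoint is each woman's own judgement that her two sides differ, and she can see and feel which side has pads. The photograph reading and the water readings are the only endpoints that are blinded or made with an instrument, so they are the main check on that judgement. Both may depend on how recently the garment came off.

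Raised pads held against the skin by compression could leave a temporary imprint. If the imprint is on one side only, the image itself tells the observer which side was padded, and concealing labels does not help. Compression or pads could also shift local tissue water for a time. With no fixed interval, such a transient effect cannot be separated from a sustained one, and no later analysis can restore a measurement condition that was never set. This is a visit procedure, so it belongs in the protocol and is not something normally left to a statistical analysis plan.

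**Working it through.** The protocol gives no figure for how long marks or fluid shifts last, so there is nothing to reproduce. The check is a comparison of its sections.

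**1. Garment state at each measurement**

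- Day zero: unworn. Photographs and water content are listed before the garment is given.
- Variable end-point visit: half-padded garment in use up to the visit; time since removal not stated.
- 3 and 6 months, women who have not declared a difference: half-padded garment; time since removal not stated.
- 3 and 6 months, women who have declared a difference: garment padded on both sides; time since removal not stated.

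**2. How far time since removal can vary.** The minimum wear is 8 hours in 24. Assume a woman wears exactly the minimum, in one block, at the same hours each day. Her time off is then 24 − 8 = 16 hours. Depending on when her appointment falls, time since removal can be anything from 0 hours (she arrives in the garment) to 16 hours. It can also differ between her own visits if the appointment hour or her routine changes.

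**3. Does the wear question close the gap?** It asks about routine, including the hours of day. That records habit. It does not standardise the state of the skin, and it does not clearly capture the removal time on the visit day.

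**4. Which comparison is exposed to what**

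- *Unmasking or altered surface from one-sided marks.* For the photograph endpoint this is confined to women still in the half-padded garment at 3 or 6 months. Women already swapped have pads on both sides. Photographs from the variable end-point visit are taken after half-padded wear, but that visit is not among the 0, 3 and 6 month time points listed for this endpoint.
- *Left-right contrast.* Both sides are compressed, so an acute effect of compression largely cancels. An acute effect of the pads, present on one side, does not.
- *Change from day zero.* Baseline is unworn, so acute compression does not cancel here, whichever garment is worn. Both secondary endpoints are worded as changes.

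**5. Direction.** An observer who recognises pad marks might favour that side. One who does not might grade fresh indentations as worse dimpling. The documents support neither direction over the other.

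**The case against.** The strongest reply is that both mechanisms are assumed. The protocol does not say that the pads mark the skin, that marks would outlast undressing and set-up, that water readings move after removal, or that women arrive in the garment. Its title calls the pads ink-printed micro-pads. This stands: it leaves the size unknown, though not the missing condition.

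Secondly, the participant information sheet is attached to the protocol but is not in the text available here, and it might carry a visit-day instruction. This also stands, and the point is limited to the protocol body.

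Thirdly, asking when the garment is worn gives some basis for a sensitivity analysis. That is partly right, but habit is not the removal time on the day.

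A reader might go further in two ways that the documents do not support:

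- *That a definite inflation of the false-positive rate follows, for example by supposing that some share of 60 women show marks and that observers vote for the marked side.* The protocol states no left-right vote and no such test. The 60 is a recruitment maximum. Swapped women would not be expected to carry one-sided marks, and neither the share marked nor the direction of any preference is given.
- *That the trial will present acute compression as a lasting benefit.* The protocol claims no lasting effect, and its stated question is pads against compression alone, where compression common to both sides largely cancels.

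**Conclusion.** The point holds as a gap in measurement conditions. Baseline is unworn, all three follow-up visits leave time since removal open, and wearing times are the woman's choice. The protocol standardises view, posture and muscle state but omits the condition most specific to a worn garment.

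The consequences are possibilities: unmasking or an altered surface in women not yet swapped, an acute pad effect in the left-right contrast, and acute compression in the change from day zero. They rest on the assumption that marks or fluid shifts occur and persist until measurement. No magnitude can be given, and the direction is open. Only secondary endpoints are affected, so the point is minor, but it is cheap to settle beforehand and cannot be repaired afterwards.

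**What to change.** - Take photographs and water readings at the variable end-point, 3-month and 6-month visits under one fixed condition of time since garment removal. The sponsor sets and justifies the length and puts it in the visit instructions. If the participant information sheet already has such an instruction, bring it into the protocol.
- Record the actual removal time on the visit day, in addition to the routine question.
- Have the coordinator check for visible pad marks and delay photography until they fade. If an image is still marked, flag it for a sensitivity analysis and keep it in the main reading. Dropping marked images would select on recent or close-fitting wear and could introduce a bias of its own.

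The cost is a line in the visit instructions, a removal-time field and a mark flag on the form, plus minor inconvenience and possibly a short wait for participants on visit days.

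### The primary endpoint counts any self-noticed right-left difference, and the variable visit lists no item recording which side the woman judges better, so events alone cannot show that Vari-pads add to compression

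*Protocol*

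**What the plan says.** The aim, under The product being tested, is to learn "whether the subjective and objective improvement is due to the compression alone, or whether the Vari-pads on the inside of the product enhance" the result. To test this, garments are made so that "the Vari-pads are printed onto the inner aspects as per usual on one side only, but not on the other side". Each woman is thus her own control, with compression on both sides and pads on one.

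The primary endpoint is "The time taken for patients to notice a self-determined significant difference between their right and left side and request the full garment". The trigger is also described in three other places:

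- The product being tested: "If and when they notice a difference between the appearance of cellulite between the two sides, they will notify us".
- The list of four visits, item 4: the visit takes place "whenever the subject can tell that there is a difference between the left and right sides".
- Variable End-point Visit: a significant difference between the sides, seen or felt, leads the woman to make contact.

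On the consequence of a report, the background says that "they will notify us and we will then swap them into the 'normal' garments with Vari-pads on both sides". Of women who never report, the visit list says "they will only have 3 visits and will not need the garment with Vari-pads on both sides".

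At issue of the garment the Protocol says "They will then be given the garment (x2) with one side covered with the Vari-pads, with the other side without any raised pads". It does not say whether the padded side is left, right or varied, and lists no item that records it.

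**The concern.** The question has a direction and the endpoint does not. A woman who finds the padded side better, one who finds the unpadded side better, and one who starts to notice an asymmetry she always had can all meet the written trigger. There is no separate control group, so the only comparison is between a woman's two sides. If the primary event does not carry the direction of that comparison, the within-woman control drops out of the primary result.

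A substantial number of events or a short median time could then be read as evidence for the pads when it is only evidence that women noticed a difference. An analysis plan cannot repair this afterwards. If the woman is not asked before she changes to both-sided garments, her judgement at the time of the event may be gone.

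**Working it through.** The Protocol has no power calculation or event-rate assumption to reproduce. The check is to compare the texts and then illustrate with assumed figures.

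**1. Is direction fixed anywhere?**

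| Place in the Protocol | What it requires | Padded side must be better? |
|---|---|---|
| The product being tested (trigger) | a difference in appearance | No |
| Visit list, item 4 | a difference between left and right | No |
| Variable End-point Visit | a significant difference, seen or felt | No |
| Primary endpoint | a self-determined significant difference, plus a request for the full garment | Not stated; implied in part by the request |

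The wording also varies: two places require a difference and two require a significant one. This is minor, but it changes when an event occurs.

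**2. Is direction recorded anywhere?** The variable visit lists weight, photographs, questions on wearing routine, water content, the Celluqol questionnaire and the issue of two new both-sided garments. None is described as asking which side is better. The day-zero list has no side-by-side rating.

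**3. Does the request supply the direction?** The background makes the swap follow from notifying a difference, and the variable visit lists both-sided garments for every woman who attends it. Neither sets a condition on which side looked better.

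**4. What the undirected endpoint can hide.**

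Inputs: 60 women (4 sizes x 15 = 60, Inclusion Criteria). The event counts and splits below are assumptions.

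A time-to-event curve uses only the event times and the numbers at risk. The better side does not enter it, so two data sets with the same times and different directions give the same curve.

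*Assume 40 events* (40/60 = 67% of women). Padded-better share = padded-better events / all events, with exact (Clopper-Pearson) limits:

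| Padded / unpadded better | Events | Share | Exact 95% CI |
|---|---|---|---|
| 36 / 4 | 40 | 36/40 = 90% | 76% to 97% |
| 20 / 20 | 40 | 20/40 = 50% | 34% to 66% |

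*Assume instead that half of the women have an event.* P(event) = P(padded better) + P(unpadded better):

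- 0.40 + 0.10 = 0.50; expected events 60 x 0.50 = 30; padded-better share 0.40/0.50 = 80%.
- 0.25 + 0.25 = 0.50; expected events 30; padded-better share 0.25/0.50 = 50%.

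In both illustrations a clear pad preference and no preference at all give the same event count, and can give the same curve.

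**The case against.** The strongest reply is that the endpoint has two conditions. A woman must notice a difference and also ask for a garment with pads on both sides, and one whose unpadded side looked better has little reason to ask for more pads. This has weight: it makes a large excess of unpadded-better events unlikely. A reader might infer that the endpoint would look just the same if the pads made cellulite worse. The wording does not formally exclude that, but the request clause makes it a strained reading and the point does not depend on it. The realistic ambiguity is between benefit and no pad effect. That ambiguity remains, because the full garment follows any reported difference.

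A second reply is that direction can be recovered from other data. Photographs and water readings are listed at the variable visit and might be read by side, and the padded side is a physical feature of the garment that could be checked later. A reader should therefore not infer that all information on direction is lost. What these sources do not give is the woman's own judgement, which is what defines the event. The blinded photograph endpoint also lists 0, 3 and 6 months, not the variable visit.

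Thirdly, the subject information sheet and consent form are attached to the Protocol but not shown, and may tell women what to report. It cannot be claimed that women receive no such instruction, only that the Protocol text does not require direction to be recorded.

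Finally, tests and models may properly be left to an analysis plan. What counts as the primary event, and what is asked when it occurs, belong in the Protocol.

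**Conclusion.** The point stands, and should be settled before further variable visits take place. Followed exactly, the Protocol can return the same primary result whether or not the pads add anything to compression. In the illustration, the same curve from 40 events is compatible with a padded-better share of 90% (95% CI 76-97%) or 50% (34-66%). These counts and splits are assumptions that show the ambiguity; they do not predict the trial's result.

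The conclusion is limited to the primary endpoint taken alone. It does not say that the secondary measures are uninformative, that the padded side can never be established, or that the pads do not work. It rests on the endpoint and trigger wording, on the listed items of the variable visit, and on the swap following any reported difference.

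**What to change.** 1. Record each woman's padded side (left or right) when the garment is issued. If it is the same side for all women, state that natural asymmetry is confounded with the pads.
2. At the variable visit, before new garments are given, ask one fixed question: left better, right better, or no clear difference.
3. Define the primary event as a self-initiated report that the padded side is better, and report unpadded-better events separately.
4. Use one trigger wording in the background, the visit list, the visit description and the endpoint.

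The cost is Protocol wording, one recorded item and one short question, with no extra visits or participants. The swap itself need not change.

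There are three downsides to state openly:

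- Reports in the wrong direction no longer count as events, so the event count may fall.
- Expectation bias remains, because women may know which side is padded.
- The question at the variable visit does not show what asymmetry was present at the start. A side question at day zero or at scheduled visits could address that, but it may prompt women to compare their sides and so alter later self-initiated reports. If such a question is added, this risk should be disclosed.

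### The sole primary endpoint is judged by a wearer who can tell which side is padded, and the planned blinded photograph reading omits the visit that could check her judgement

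*Protocol*

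**What the plan says.** The Protocol's section on the product being tested sets the question: is the improvement due to compression alone, or "whether the Vari-pads on the inside of the product enhance the subjective or objective impression of cellulite"? Each woman is her own control. Under First Visit, "They will then be given the garment (x2) with one side covered with the Vari-pads, with the other side without any raised pads". The product section describes the pads as "small, raised pads ('Vari-pads') of different heights printed on the inner aspect", and The Trial adds that "to increase the area of contact between garment and cellulite, we suggest wearing a thong" or similar underwear.

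One primary endpoint is listed: "The time taken for patients to notice a self-determined significant difference between their right and left side and request the full garment". The section on the Variable End-point Visit gives the trigger: "When subjects can see or feel a significant difference in the cellulite of their buttocks and/or thighs between the sides, they will contact us". At that visit photographs and water measurements are taken, and then "They will be given 2 new garments with Vari-pads on BOTH sides".

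Under Secondary endpoints, two blinded observers assess change in photographs at 0, 3 and 6 months, and transcutaneous water is a further measure. The variable end-point visit is not among the times listed for the blinded reading. Nothing in the Protocol links either measure to the primary event.

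**The concern.** The within-woman design deals well with compression, which both sides receive. It does not deal with the wearer's knowledge of which side is treated. That knowledge differs between the sides exactly as the pads do, so a wearer-judged difference may reflect either one. Randomising the padded side, recording which side looks better, or removing the new garments that follow a declaration would not separate them.

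The planned evidence that could separate them is a side-to-side reading by observers who do not know which side was padded. For a woman who declares, the photographs that matter are those taken just before her swap, and these fall outside the listed blinded reading. Once she has swapped, both sides carry pads, and her later photographs no longer isolate the effect of padding one side.

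At stake is the causal part of the aim: whether the pads add anything to compression.

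**Working it through.** **Is the wearer unmasked?** The Protocol does not say that she is told the side. It follows from three points:
- The pads are raised, lie on the inner face, and are present on one side only; the other side has no sham.
- The suggested underwear increases contact with the garment.
- The event consists partly of asking for the fully padded garment, so she must know that hers is half-padded.

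**What confirms the event?** Nothing beyond the wearer. The trigger is sight or feel, with no threshold, assessor or measurement.

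**Photographs set against garment worn**

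| Visit | Garment worn up to the visit | Photographs taken | In the listed blinded reading |
|---|---|---|---|
| Day zero | none | yes | yes |
| Variable end-point | half-padded | yes | no |
| 3 months | half-padded, or bilateral if already swapped | yes | yes |
| 6 months | half-padded, or bilateral if already swapped | yes | yes |

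A woman who declares before month 3 has no half-padded photograph in the listed reading. One who declares between months 3 and 6 has only her 3-month set.

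**Sample size.** The stated 60 reproduces as 4 sizes × 15. It is a supply limit. No alpha, power or effect size is given, so there is no power calculation to check.

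**Illustration on the endpoint itself (assumed rates, no pad effect).** If expectation alone leads a constant share h of women still wearing the half-padded garment to declare each month, the share declaring by six months is 1 − (1 − h)^6.

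| h per month | Share by 6 months | Events among 60 |
|---|---|---|
| 2% | 11% | 7 |
| 5% | 27% | 16 |
| 10% | 47% | 28 |
| 20% | 74% | 44 |

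**Illustration on a hypothetical test.** Suppose instead that declaring women named the better side and an exact two-sided 5% binomial test were applied. The Protocol contains no such test. The critical count is the smallest r with P(X ≥ r | n, 0.5) ≤ 0.025.

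| n | r | P(X ≥ r) at 50% | at 60% | at 70% | at 80% |
|---|---|---|---|---|---|
| 40 | 27 | 1.9% | 21% | 70% | 98% |
| 60 | 39 | 1.4% | 26% | 84% | 99.8% |

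The last three columns are the chance of wrongly favouring the pads when expectation alone makes that share of women name the padded side.

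**Which rule for the blinded reading?** Take one left/right choice per woman and a 50% chance of choosing either side if there is no effect.
- Simple majority: [1 − P(X = n/2)] / 2. For n = 40, (1 − 0.125)/2 = 44%. For n = 60, (1 − 0.103)/2 = 45%.
- Simple majority added to the hypothetical wearer test, taking the two as independent: n = 40 gives 0.44 × (21%, 70%, 98%) ≈ 9%, 31%, 43%; n = 60 gives 0.45 × (26%, 84%, 99.8%) ≈ 12%, 38%, 45%. A majority rule is too weak.
- Two-sided 5% test: 27 of 40 or 39 of 60 choices are needed. False claims in favour of the pads are 1.9% or 1.4%, and the wearer's opinion does not enter the calculation.

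**The case against.** **Perception is a fair target for a retail garment.** The aim says subjective or objective, and a wearer-judged endpoint answers the first. This stands, and is the reason to keep the endpoint. It does not settle the causal question, because even a subjective effect of the pads has to be distinguished from knowing where they are.

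**Pads can hardly be masked.** Probably so. The point does not ask for masking of the wearer, only for a reading by observers who are already planned.

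**A decision rule may sit in an analysis plan not shown here.** This stands. The absence of an agreement rule from the Protocol is not itself the fault. The Protocol does fix the choice of an unmasked, self-judged sole primary endpoint and the times of the blinded reading.

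**Two stronger readings go too far.** A reader might take 21%, 70% and 98% as this trial's false-positive rates. They are not: the endpoint is time to noticing a difference, it does not ask which side is better, and no record of the better side is described. A reader might also infer that the trial will declare the pads effective on the primary result while disregarding its observers. The Protocol states no success rule, so that is not supported either. The blinded and instrument measures exist and could contradict a positive primary result.

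**Conclusion.** The point holds in a limited form. The sole primary endpoint is open to expectation bias by construction and cannot, by itself, show that the pads add to compression. The planned blinded reading omits the last half-padded photographs of every woman who swaps at the variable end-point visit.

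The size of the bias cannot be derived from the document. The range of 7 to 44 expectation-driven events among 60 rests on assumed monthly rates of 2% to 20%. The 21/70/98% figures rest on an assumed test, 40 assumed declarers and assumed bias levels, and should be carried only with that label.

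The 1.9% and 1.4% error rates for the repaired reading assume one choice per woman, observers who are truly unaware of the padded side, and an even chance of either side being chosen if the pads do nothing. The last assumption needs the padded side, and the moment at which she declares, to be unrelated to chance or pre-existing differences between her two sides.

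**What to change.** 1. Keep the wearer-reported primary endpoint. State that, taken alone, it is reported as a difference perceived by unmasked wearers.
2. Add the variable end-point visit to the blinded reading. The two observers, unaware of the padded side, compare left with right on each woman's last photographs before any swap to bilateral pads: the variable end-point visit, or the 6-month visit if she never declares.
3. State in advance how ties and disagreement between the observers are counted.
4. Conclude that the pads add to compression only if this reading favours the padded side on a two-sided 5% test (27 of 40, or 39 of 60), not on a simple majority.

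**Cost.** More than a change of wording: a new reading time and a new observer task, a side-to-side choice in addition to change over time. The photographs are already taken, so no visit or device is added. The claim also becomes harder to reach. If observers truly chose the padded side for 70% of women, the rule would be met about 70% of the time with 40 readings and 84% with 60 (same binomial tails as above).
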